5.6 Restrictions

5.6.1 Prohibited Medications

All aspirin, NSAIDs, herbs, natural medications, or any other drug with platelet inhibitory properties must be discontinued at least 1 week prior to elective surgical or other invasive procedure and for the duration of treatment with LR769.

Additional restrictions to concomitant therapies include the use of other sources of FVIIa, such as aPCC (FEIBA[®]) or NovoSeven[®]. These products may be used only if the response to LR769 is considered insufficient (ie, treatment failure), in which case these bypassing agents may be used for rescue therapy.

Other agents for the prevention of excessive bleeding during surgical or other invasive procedures, such as antifibrinolytics, are allowed and will be recorded on the eCRF.

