7.3 Handling of Missing Data

Any imputation of missing or incomplete data will be flagged in the analysis datasets. The original value will be kept for traceability.

Missing Final Assessment of Postoperative Response (48 [\pm 4] hours after the last dose of LR769)

In accordance with the definition of postoperative assessment in section 6.8 of the Protocol, missing final postoperative assessment of treatment response by the investigator will be imputed to "Poor", if and only if, both of the following conditions are satisfied: (1) patient was withdrawn from study, within 2 days after the last dose of LR769, due to adverse event or by Investigator's decision and (2) rescue therapy (any medication in antihemorrhagics ATC subgroup) was used within 52 hours after the last dose of LR769.

Incomplete/Missing Dates

Dates of historical events such as the date of diagnosis, date of onset, start/stop dates of previous treatment, start dates of medical conditions, etc. will be imputed when partial dates are collected. In case of missing month and day and available year YYYY the corresponding date will be replaced with "01JULYYYY". In case of missing day the date will be replaced with "15MMMYYYY".

The following rules will be applied for AEs and concomitant medications with incomplete dates:

- If Day is missing for Start Date and Month and Year are the same as Month and Year for the First Treatment Date, then Start Date equals First Treatment Date.
- If Day is missing for Start Date and Month and Year are not the same as Month and Year for the First Treatment Date, then impute Day 1 of the month.
- If Day and Month are missing for Start Date and the Year is the same as the Year for the First Treatment Date, then Start Date equals First Treatment Date.
- If Day and Month are missing for Start Date and the Year is not the same as the Year for the First Treatment Date, then impute July 1st of the year.

- If the Start Date is missing entirely, impute the start date with minimum between the End date of AE and First Treatment Date. Therefore, if an AE with missing start date has ended before the start of the treatment, the Start Date will be imputed with the End Date, and if the AE in question ended after the First Treatment Date, then the Start Date will be imputed with the First Treatment Date.

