7.7 Efficacy Endpoints and Analysis

All the Efficacy analyses will be stratified by surgery type and overall. All analyses will then be repeated stratifying by age group (< 12 years and \geq 12 years). Efficacy population will be used for all the analyses described in this section.

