7.7.1 Analysis of Primary Efficacy Endpoint

The primary efficacy endpoint is the percentage of surgical or other invasive procedures with a “good” or “excellent” response to LR769 treatment, as assessed by the investigator at the study center 48 (\pm 4) hours after the last administration of LR769; this assessment will be based upon the totality of assessments performed on the patient at each timepoint, also taking into consideration the surgeon’s intraoperative hemostatic assessment, the number of (interventions for) bleeding episodes, oozing, blood transfusions, and the amount of LR769 used. An additional sensitivity analysis will be performed in which patients whose 48-hour assessment is missing are treated as failures.

The proportion of “good” and “excellent” responses at 48 (\pm 4) hours will be summarized. Clopper-Pearson exact 95% confidence interval for proportion will be calculated for each surgery type and age group and overall. The summaries will include missing assessments in percent calculation, while they will still be discarded when calculating the proportion of successes and the confidence interval (CI). The missing values imputed as per section 7.3 of this SAP will be analyzed as imputed.

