7.9.2 Concomitant Medications

Concomitant medications will be coded with WHO DD providing ATC2 and ATC4 codes, and PT for each medication. A medication will be considered concomitant if it has started during the treatment period, or if it has started prior to the first treatment and ended within the treatment period. The number and percentage of patients taking concomitant medications will be summarized by surgery type and overall and by ATC codes for the Safety Population.

A data listing of concomitant medications will be provided.

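### Other agents to prevent bleeding are permitted alongside LR769, but no pre-specified efficacy table shows response by their use, and SAP 7.3 does not separate permitted prophylaxis from rescue

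*Protocol*

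**What the plan says.** Protocol 5.6.1 bars drugs that inhibit platelets and continues: "Additional restrictions to concomitant therapies include the use of other sources of FVIIa", which may be used only when LR769 has failed. It then states: "Other agents for the prevention of excessive bleeding during surgical or other invasive procedures, such as antifibrinolytics, are allowed", and has their use entered on the eCRF. Protocol 5.5 and 6.11 require date, time and dose of all concomitant therapy.

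The primary endpoint (protocol 9.5.1, SAP 7.7.1) is the share of procedures that the investigator rates good or excellent 48 hours after the last dose. The factors behind that rating include the surgeon's assessment, bleeding episodes, "oozing, blood transfusions, and the amount of LR769 used". Other hemostatic agents are not among them.

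SAP 7.7 says "All the Efficacy analyses will be stratified by surgery type and overall", then repeats everything by age group. The only sensitivity analysis of the primary endpoint concerns missing 48-hour ratings. Co-medication is covered in SAP 7.9.2: "The number and percentage of patients taking concomitant medications will be summarized by surgery type and overall and by ATC codes", for the Safety Population, plus a listing.

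SAP 7.3 imputes a missing final rating as Poor when two conditions both hold. One is withdrawal within 2 days of the last dose because of an adverse event or by the investigator's decision. The other is use, within 52 hours of the last dose, of "rescue therapy (any medication in antihemorrhagics ATC subgroup").

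**The concern.** The primary objective is the efficacy of LR769 in preventing excessive bleeding. The permitted agents are given for the same purpose, and no control arm carries the same background treatment. If they were used in many procedures, the success rate would describe LR769 plus whatever else was given. A reader of the planned tables could not see whether the rate also held when LR769 was the only hemostatic agent.

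A related inconsistency lies in the imputation. A permitted preventive agent plays no part in the primary summary, yet the same agent can serve as the marker of failure when a final rating is missing.

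**Working it through.** **1. Is there any planned table of response by co-treatment?** The splits in SAP 7.7 and 7.7.1 are surgery type, age group and overall. The sensitivity analysis changes only the handling of missing ratings. SAP 7.9.2 counts patients by ATC code and does not cross this with response. So there is none.

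**2. Is the concomitant-medication table complete?** SAP 7.9.2 counts a drug if it started during treatment, or if it started before the first dose and stopped during treatment. A drug started before the first dose and continued past the last meets neither condition. A preventive agent begun before surgery and continued after LR769 would be missing from the table.

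**3. What could the pooled figure hide?** The plan gives no co-use rate, success rate or precision target, so there is no figure of its own to reproduce. The only planned number is the minimum of 12 procedures (SAP section 4). The following is illustration under assumptions. Clopper-Pearson 95% limits for x successes in n are the 0.025 quantile of Beta(x, n−x+1) and the 0.975 quantile of Beta(x+1, n−x).

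Assume 11/12 successes: 91.7% (61.5 to 99.8). The result without a co-agent depends on how many procedures were co-treated and where the one failure fell:

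| Co-treated (assumed) | Failure among those without a co-agent | Failure among those co-treated |
|---|---|---|
| 3 of 12 | 8/9 = 88.9% (51.8 to 99.7) | 9/9 = 100% (66.4 to 100) |
| 6 of 12 | 5/6 = 83.3% (35.9 to 99.6) | 6/6 = 100% (54.1 to 100) |
| 9 of 12 | 2/3 = 66.7% (9.4 to 99.2) | 3/3 = 100% (29.2 to 100) |

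All six cells give the same pooled figure.

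The same in expectation: pooled rate = f × p(co-treated) + (1 − f) × p(without), where f is the co-treated share. With assumed rates of 95% and 70%, f = 0, 0.25, 0.50 and 0.75 give 70%, 76.25%, 82.5% and 88.75%.

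**4. When does SAP 7.3 misclassify?** Three things must coincide: a missing final rating, withdrawal for one of the two stated reasons within 2 days, and an antihemorrhagic in the 52-hour window (48 + 4 hours, the end of the assessment window). Nothing asks why the agent was given. The documents do not list the members of the ATC subgroup; that it takes in permitted preventive agents is a plain reading of the class name and is an assumption here.

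Size for one such case, with 11 other procedures all successes:
- not imputed, the missing rating is dropped: 11/11 = 100%, lower limit 0.025^(1/11) = 71.5%;
- imputed Poor: 11/12 = 91.7% (61.5 to 99.8);
- in the SAP's sensitivity analysis: 11/12 either way.

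**5. How do the rescue passages compare?** Protocol 5.6.1 allows bypassing agents as rescue after treatment failure. The Poor category in protocol 6.8 names a bypassing agent or porcine FVIII. Protocol 6.13 goes further and leaves room for other kinds of hemostatic treatment. SAP 7.3 claims to follow 6.8 but uses a whole drug class regardless of the reason for use. The four passages do not agree and need to be reconciled.

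**The case against.** The strongest reply is that the study is descriptive and has no success threshold, co-agents are openly permitted and recorded, and the data can be linked. SAP 7.9.2 promises a concomitant-medication listing, SAP 7.7.2 a listing of response assessments, and SAP 7.1 a listing of all collected data. With about 12 procedures, a reader could match them by hand. This stands. A reader might infer that co-medication cannot be tied to a procedure's outcome, but that is true only of the planned summary tables.

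A split would also be weak evidence. If 6 of 12 procedures were co-treated and the results were 6/6 (54.1 to 100) against 4/6 (22.3 to 95.7), the two-sided Fisher p-value would be 2 × C(6,2)/C(12,2) = 30/66 = 0.45. Use is not randomised and may follow procedure type and bleeding risk. This stands too and limits the table to description. The SAP already accepts that limit for its surgery and age splits.

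A simple yes/no flag for any other agent given between surgery and the final rating would do harm. It would move procedures in which an agent was added because of bleeding into the co-treated group, flattering LR769 without co-agents, and would miss agents given only before surgery. Hence the narrower definition under the fix.

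On SAP 7.3, a reader might infer that routine prophylaxis alone turns a missing rating into Poor, or that the protocol confines rescue to bypassing agents and porcine FVIII. Neither is supported. The rule also requires withdrawal and never alters an observed rating, and protocol 6.13 describes rescue more broadly.

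**Conclusion.** The point holds as a gap in pre-specification. Other preventive agents are permitted in a single-arm trial, and no planned efficacy summary shows response by their use. A reader might go further and conclude that success due to co-treatment is being credited to LR769. The documents do not support that: they give neither the frequency nor the effect of such agents, and the range in the working rests on assumed allocations that could run in either direction.

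The omission in SAP 7.9.2 follows directly from its wording. The SAP 7.3 problem is real but narrow. It affects only missing ratings with a qualifying withdrawal, works against LR769, and assumes that the permitted agents fall in the antihemorrhagics subgroup. The remedies are worth making because they are specific and cheap, not because a bias has been demonstrated.

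**What to change.** 1. **SAP 7.7.1:** add a descriptive table of the primary endpoint by planned preventive use of another hemostatic agent (yes/no), with Clopper-Pearson intervals. Count agents started before or during the procedure for prevention and not in response to bleeding. Report agents started because of bleeding separately. List agent, timing and reason beside each procedure's rating.
2. **SAP 7.3:** for the imputation, count as rescue only hemostatic agents started because of bleeding or inadequate response, and reconcile the wording with protocol 5.6.1, 6.8 and 6.13. This changes an analysis definition, not any treatment rule.
3. **SAP 7.9.2:** count any drug taken during the treatment period as concomitant, whenever it started or stopped.

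Cost: one table, one listing and two wording changes. Agent, date, time and dose are already collected. Protocol 5.5 and 6.11 do not list the reason for use, so if the eCRF does not hold it, a short medical review is needed, ideally done without sight of the ratings. The drawback is small, non-randomised subgroups with wide intervals, and the table should say that it is for description only.

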5.6.2 Prior Therapy

At least 24 hours must have passed between the last administration of a FVIIa-containing product (aPCC (FEIBA[®]) or (NovoSeven[®])) and the first LR769 administration.

5.6.3 Prior Gastrointestinal Distress/Ulcers

Patients with active gastric or duodenal ulcer disease are not allowed to participate in this study, in accordance with [Exclusion Criterion 13](#).

5.6.4 Fluid and Food Intake

No restrictions on fluid or food intake apply.

5.6.5 Patient Activity Restrictions

Patients should not undergo physical therapy before the fourth day post-surgical or invasive procedure. If physical therapy is planned, an IV bolus dose of 75 µg/kg of LR769 administered within ≤ 2 minutes is recommended each time before the therapy begins. Similarly, before drain or suture removal, an IV bolus dose of 75 µg/kg of LR769 administered within ≤ 2 minutes is recommended.

5.7 Treatment Compliance

All patients will be treated with LR769 in the hospital or outpatient treatment center prior to, during, and immediately after the surgical or other invasive procedure. Patients may be discharged from the hospital or outpatient treatment center and treated at home at the investigator's discretion. During the patient's hospitalization for the procedure, compliance is managed by the site staff. If the patient continues treatment with LR769 after discharge from the hospital or outpatient treatment center, he will be given a patient diary in which to record the exact dose and time of LR769 administration.

5.8 Packaging and Labeling

LR769 will be supplied in clear glass vials as lyophilized powder in 1 mg and 5 mg. The vials will be labeled using multilingual labels which will comply with local regulations and requirements. Vials will be packed in an outer box. In addition, prefilled syringes with water for injection for reconstitution as well as supplies for reconstitution and administration of LR769 will be provided. Study staff will refer to a separate Pharmacy Manual that will describe the appropriate directions, and patients will refer to "Instructions for Use." if discharged home while still on treatment.

5.9 Storage and Accountability

LR769 must be stored in a safe and secure place at the study center or at home. LR769 is to be stored at 36° to 86° F (2-30°C), is not to be frozen, and must be protected from light. The investigator is fully responsible for LR769 stored at the study center. Access at the study center will be strictly limited to the investigator and designated staff. Neither the investigator nor designated staff may provide LR769 to any patient not in the study. Dispensing of LR769 may be delegated, e.g., to a hospital pharmacy, as locally applicable. Patients who are given LR769 for home administration will be instructed to return the used and any unused vials to the site.

All LR769 received at the investigational site will be documented on LR769 drug accountability forms. This documentation must be available for review by the monitor at the monitoring visit to confirm proper LR769 management.

5.10 Investigational Product Retention at Study Site

All used and unused vials of LR769 will be retained until drug accountability has been performed by the monitor. For this purpose, the investigator or designated staff will keep all used vials, including those returned by patients who administered LR769 at home, for the accountability check by the monitor (unless local regulation does not allow this).

All unused vials will be returned or destroyed according to the instructions of the Sponsor at the end of the study. A separate pharmacy manual will be prepared that will describe the appropriate procedures.

6 STUDY PROCEDURES

6.1 Informed Consent

All patients will be informed of the aims of study, the possible AEs, the procedures and possible risks to which they will be exposed, and how treatment and dose will be determined. They will be informed as to the strict confidentiality of their personal data, and that their medical records may be reviewed for study purposes by authorized individuals other than their treating physician. It will be emphasized that participation is voluntary and that the patient is allowed to refuse further participation in the protocol whenever he wants. Once the patient completely understands the study and its procedures and risks, he will be asked to sign and date the Informed Consent. Study procedures may not begin until after the Informed Consent is signed and dated.

If the patient is younger than 18 years of age, his parent(s)/legal guardian(s) will receive the same information. His parent(s)/legal guardian(s) will sign and date the Informed Consent.

The patient may, depending on his age, receive age-appropriate information as well as be asked to sign and date an Assent form. Age of providing information and Assent form may differ among institutions and will be determined by local law and Institutional Review Board (IRB) or Independent Ethics Committee (IEC) requirements.

Once the Informed Consent and/or Assent has been signed and dated by the patient and/or parent(s)/legal guardian(s), the patient is considered enrolled in the study.

6.2 Medical History

The medical history of each patient will be obtained. Specific information will be recorded in the source records and on the eCRF relating to any prior or existing medical conditions/surgical procedures involving the following: infectious diseases (including viral infections, such as hepatitis and human immunodeficiency virus [HIV]), allergies including allergic responses to LR769 and its excipients (arginine HCl, isoleucine, trisodium citrate dihydrate, glycine, lysine HCl, polysorbate 80), metabolic/endocrine/nutritional, hematopoietic, musculoskeletal, dermatologic, head/ears/eyes/nose/throat (HEENT), breasts, respiratory, cardiovascular, gastrointestinal/hepatic, genitourinary/renal, neurologic, and psychiatric/psychosocial.

In addition, specific detailed information regarding the clinical symptoms and treatment of the hemophilia and patient bleeding history will be collected. This will include the following: type of hemophilia (A or B), history of bleeding episodes, severity (mild, moderate or severe), inhibitor level, date of first detection of inhibitors, concomitant medication use, and response to FVIII or FIX if applicable in case of either anamnestic or refractory response to factor administration.

Demographics (date of birth, race/ethnicity, and sex) will also be collected.

6.3 Physical Examination

- 6.3.1 All findings from physical examinations will be recorded on source documents and entered into the eCRF. The standard physical examination will include the following observations / measurements: height, weight, general appearance, skin, HEENT, lymph nodes, heart, lungs, abdomen, extremities/joints, neurological, and mental status. Postoperative Assessments

The patient will be followed postoperatively according to the site's standard of care. Postoperative assessments include assessing patient's incision or procedure site for inflammation, bleeding, infection, oozing, and discoloration.

6.4 Vital Signs

Vital signs will include systolic and diastolic blood pressures (mmHg), heart rate (beats/minute), respiratory rate (breaths/minute), and body temperature (°C or °F, sublingual or tympanic).

6.5 Electrocardiography

6.5.1 12-Lead Electrocardiograms

A standard 12-lead electrocardiogram (ECG) will be performed in supine position at Screening, and will be reviewed for any clinically relevant abnormalities by a qualified physician prior to the first administration of LR769.

6.6 Clinical Laboratory Tests

After the sponsor authorizes enrollment of patients <12 years old, the investigator will contact the Medical Monitor regarding any such patient for adaptation of the blood sample schedule to the patient's body weight in consideration of ICH Harmonised Tripartite Guideline "Clinical Investigations of Medicinal Products in the Paediatric Population, ICH Topic E 11,"

(http://www.ema.europa.eu/docs/en_GB/document_library/Scientific_guideline/2009/09/WC500002926.pdf). Blood volume drawn cannot exceed 3% of the total blood volume of the patient during a period of 4 weeks and cannot exceed 1% of the total blood volume at any single time.

If the local lab is unable to perform analyses from the recommended volumes, the PSI medical monitor or lab specialist should be contacted in order to discuss possible volumes. In such cases blood volumes will be calculated individually, taking into account patient's weight and applicable requirements in order not to exceed 1% at any single time and 3% within 4 weeks.

Table 3 includes estimates for the amount of blood to be drawn for pediatric patients who weigh <12 kg.

Table 3. Total Amounts (mL) of Blood Taken During the Study for Patients <12 kg

	Screen ^a	Pre Surgery	24 hrs post procedure	7-14 days post first dose	48 hrs post last dose	28 days post last dose/EOS
Hematology	1		1		1	1
PT and aPTT (local lab)	3					
Chemistry	2		2		2	2
Factors VIII or IX, and Inhibitors (central lab only)	2.8					
Immunogenicity and serum storage sample		2				3
Immunogenicity				1.2	1.2	
Totals	8.8	2	3	1.2	4.2	6

EOS = end of study

^a Screening visit will be split into 2 different days if the total volume of blood drawn is to exceed 0.8 mL/kg at a single time.

Serology not performed for pediatric patients < 12 kg.

Table 4 includes estimates for the amount of blood to be drawn for pediatric patients who weigh ≥12 kg and <27 kg.

Table 4. Total Amounts (mL) of Blood Taken During the Study for Pediatric Patients ≥ 12 kg and < 27 kg

	Screen ^a	Pre Surgery	24 hrs post procedure	7-14 days post first dose	48 hrs post last dose	28 days post last dose/EOS
Hematology	1		1		1	1
PT and aPTT and Factor VIII or IX and Inhibitors (local lab)	4.5					
Serology	4					
Chemistry	2		2		2	2
Factors VIII or IX and Inhibitors (central lab)	4.2					
Immunogenicity and serum storage sample		3				4
Immunogenicity				2	2	
Totals	15.7	3	3	2	5	7

EOS = end of study

^a Screening visit will be split into 2 different days if the total volume of blood drawn is to exceed 0.8 mL/kg at a single time.

Table 5 includes estimates for the amount of blood to be drawn for pediatric patients who weigh ≥ 27 kg.

Table 5. Total Amounts (mL) of Blood Taken During the Study for Pediatric Patients ≥ 27 kg

	Screen	Pre Surgery	24 hrs post procedure	7-14 days post first dose	48 hrs post last dose	28 days post last dose/EOS
Hematology	2		3		3	3
PT and aPTT and Factors VIII and IX and Inhibitors (local lab)	6					
Serology	4					
Chemistry	4		5		5	5
Factors VIII or IX and Inhibitors (central lab)	4.2					
Immunogenicity and serum storage sample		3				4
Immunogenicity				2	2	
Totals	20.2	3	8	2	10	12

EOS = end of study

Table 6 includes estimates for the amount of blood to be drawn for adult patients (≥ 18 years old).

Table 6. Total Amounts (mL) of Blood Taken During the Study for Adult Patients (≥ 18 Years)

	Screen	Pre surgery	24 hours post procedure	7-14 days post first dose	48 hours post last dose	28 days post last dose/EOS
Hematology	4		4		4	4
PT and aPTT and Factors VIII and IX and Inhibitors (local lab)	8					
Serology	6					
Chemistry	8		8		5	5
Factors VIII or IX and Inhibitors (central lab)	5.7					
Immunogenicity, serum storage sample		5				5
Immunogenicity				3	3	
Totals	31.7	5	12	3	12	14

EOS = end of study

